### **Overdose**

Any dose of study drug administered in excess of that specified in this protocol is considered to be an overdose. Signs and symptoms of an overdose that meet any SAE criterion must be reported as a SAE in the appropriate time frame ( see Section 6.2.2) and documented as clinical sequelae to an overdose.

There is no specific experience in the management of acalabrutinib overdose in patients.

### **Dose Modification for Hepatic Impaired Subjects (Child-Pugh Criteria)**

Acalabrutinib is metabolized in the liver. Please see the Child-Pugh scoring system outlined in Appendix G to determine whether dose modifications are warranted according to the following instructions. For patients who develop mild-moderate liver impairment while on study (Child-Pugh class A), the recommended dose is acalabrutinib 100 mg daily. Patients who develop severe hepatic impairment (Child-Pugh class C) must hold study drug until resolved to moderate impairment (Child-Pugh class B) or better and may be re-treated according to resolved hepatic conditions. Monitor patients for signs of toxicity and follow dose modification guidance as needed.

## **3.9 CONCOMITANT THERAPY**

### **3.9.1 Permitted Concomitant Therapy**

Supportive medications in accordance with standard practice (such as for emesis, diarrhea, etc.) are permitted. Use of neutrophil growth factors (filgrastim and pegfilgrastim) or red blood cell growth factors (erythropoietin) is permitted per institutional policy and in accordance with the ASCO guidelines. Transfusions may be given in accordance with institutional policy.

Short courses ( $\leq$ 14 days) of steroid treatment that do not exceed 100 mg per day of prednisone or equivalent are permitted.

Treatment for autoimmune cytopenias are permitted for  $<$ 14 days at doses that do not exceed 100 mg per day of prednisone or equivalent.

The following may be considered: localized hormonal or bone sparing treatment for non-B-cell malignancies, and localized radiotherapy for medical conditions other than the underlying B-cell malignancies.

### **3.9.2 Prohibited or Restricted Concomitant Therapy**

Any non-study related chemotherapy, anticancer immunotherapy, corticosteroids (at dosages equivalent to prednisone  $>$ 100 mg/day for longer than 2 weeks), experimental therapy, or radiotherapy for treating DLBCL are prohibited.

Warfarin or equivalent vitamin K antagonists (eg, phenprocoumon) are prohibited.

For additional information on drugs with potential drug-drug interactions, refer to Section 3.10.2.

### **3.9.2.1 CYP Inhibiting/Inducing Drugs**

Based on available nonclinical and clinical data, acalabrutinib is almost completely metabolized by multiple CYP and non CYP metabolic pathways. CYP3A-mediated oxidation is the major route of metabolism in humans. Additional studies were performed in a human liver microsomal system with specific chemical inhibitors of individual CYP isoforms. Inhibition of acalabrutinib metabolism by specific CYP3A4/5 inhibitors (ketoconazole and troleandomycin) indicate that CYP3A4/5 is the predominant CYP isoform responsible for metabolism of acalabrutinib.

PBPK modeling predicted the magnitude of changes in acalabrutinib and active metabolite exposure due to a variety of moderate CYP3A inducers and inhibitors. Avoid coadministration of strong CYP3A inhibitors (such as itraconazole and rifampin) with acalabrutinib on study, if possible. If moderate or strong CYP3A inhibitors are required on study, monitor subjects for toxicity (refer to IB section 6.7). A list of common CYP3A4/5 inhibitors or inducers is provided at <http://medicine.iupui.edu/clinpharm/ddis/table.aspx>.

- If acalabrutinib must be administered with a strong or moderate CYP3A4/5 inhibitor, the Medical Monitor should be consulted before use, and a dose reduction of acalabrutinib to 100 mg PO daily or temporarily holding acalabrutinib should be considered. Patients should be closely monitored for potential treatment-related toxicities.
- There was minimal involvement of CYP1A2, CYP2E1, CYP2B6, CYP2C8, CYP2C9, CYP2C19, or CYP2D6 in the metabolism of acalabrutinib in human liver microsomes.. Therefore drugs that are known to be CYP1A2, CYP2E1, CYP2B6, CYP2C8, CYP2C9, CYP2C19, or CYP2D6 inhibitors or inducers are not restricted.

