Concomitant Medications	
Permitted Concomitant Therapy
 
Antiemetics are permitted if clinically indicated. Standard supportive care medications are permitted as per institutional standards.
 
Supportive medications in accordance with standard practice (such as for emesis, diarrhea, etc.) are permitted. Use of neutrophil growth factors (filgrastim and pegfilgrastim) or red blood cell growth factors (erythropoietin) is permitted per institutional policy and in accordance with the ASCO guidelines. Transfusions may be given in accordance with institutional policy.
 
Short courses (<math>\leq</math>14 days) of steroid treatment for non-cancer related medical reasons (e.g., joint inflammation, asthma exacerbation, rash, antiemetic use and infusion reactions) at doses that do not exceed 100 mg per day of prednisone or equivalent are permitted.
 
Treatment for autoimmune cytopenias are permitted for <math><</math>14 days at doses that do not exceed 100 mg per day of prednisone or equivalent.
 
The following may be considered: localized hormonal or bone sparing treatment for non-B-cell malignancies, and localized radiotherapy for medical conditions other than the underlying B-cell malignancies.
 
Prohibited Concomitant Therapy
 
The concomitant use of strong inhibitors/inducers of CYP3A4 (see Appendix 3) should be avoided when possible (see Section 3.10.2). If a subject requires a strong CYP3A inhibitor while on study, monitor the subject closely for potential toxicities. For additional information on drugs with potential drug-drug interactions, refer to Section 3.10.2.
 
Any non-study related chemotherapy, anticancer immunotherapy, corticosteroids (at dosages equivalent to prednisone <math>></math> 20 mg/day for longer than 2 weeks), experimental therapy, or radiotherapy for treating DLBCL are prohibited.
 
Warfarin or equivalent vitamin K antagonists (eg, phenprocoumon) are prohibited.

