#### **3.10.2 Drug-drug Interactions & Infusion Reactions**

Acalabrutinib is metabolized by CYP3A. At the systemic exposure levels expected in this study, acalabrutinib inhibition of CYP metabolism is not anticipated.

Concomitant administration of acalabrutinib with a strong CYP3A and P-glycoprotein (P-gp) inhibitor, itraconazole increased exposure by approximately 5-fold. Conversely, concomitant administration of acalabrutinib with a strong CYP3A inducer, rifampin decrease acalabrutinib exposure and could reduce efficacy. Consequently, the concomitant use of strong inhibitors/inducers of CYP3A (see Appendix 3) should be avoided when possible.

If medically justified, subjects may be enrolled if such inhibitors or inducers can be discontinued or alternative drugs that do not affect these enzymes can be substituted within 7 days before first dose of study drug. If a subject requires a strong CYP3A4 while on study, the subject should be monitored closely for any potential toxicities.

The effect of agents that reduce gastric acidity (eg, proton pump inhibitors or antacids) on acalabrutinib absorption was evaluated in a healthy volunteer study (ACE-HV-004). Results from this study indicate that subjects should avoid the use of calcium carbonate-containing drugs or supplements for a period of at least 2 hours before and at least 2 hours after taking acalabrutinib. Use of omeprazole, esomeprazole, lansoprazole or any other proton pump inhibitors while taking acalabrutinib is not recommended due to a potential decrease in study drug exposure. However, the decision to treat with proton-pump inhibitors during the study is at the investigator's discretion, with an understanding of the potential benefit to the subject's gastrointestinal condition and a potential risk of decreased exposure to acalabrutinib.

Although the effect of H2-receptor antagonists (such as famotidine or ranitidine) on acalabrutinib absorption has not been evaluated, if treatment with an H2-receptor antagonist is required, the H2-receptor antagonist should be taken approximately 2 hours after an acalabrutinib dose.

Infusion reactions related to rituximab, etoposide, ifosfamide, or carboplatin should be managed according to the package insert and/or institutional standard of care.

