**APPENDIX 3. KNOWN STRONG IN VIVO INHIBITORS OR INDUCERS OF CYP3A**

Strong Inhibitors of CYP3Aa	Strong Inducers of CYP3Ad
boceprevir	carbamazepine e
clarithromycin b	phenytoin e
conivaptin b	rifampin e
indinavir	St John's wort e
itraconazole b	
ketoconazole b	
lopinavir/ritonavir b (combination drug)	
mibepradil c	
nefazodone	
nelfinavir	
posaconazole	
ritonavir b	
saquinavir	
telaprevir	
telithromycin	
voriconazole	

- a. A strong inhibitor is defined as an inhibitor that increases the AUC of a substrate by  $\geq$  5-fold.
- b. In vivo inhibitor of P-glycoprotein.
- c. Withdrawn from the United States market because of safety reasons.
- d. A strong inducer is defined as an inducer that results in  $\geq$  80% decrease in the AUC of a substrate.
- e. In vivo inducer of P-glycoprotein.

Note: The list of drugs in these tables is not exhaustive. Any questions about drugs not on this list should be addressed to the Sponsor of the protocol.

Source:

FDA Drug Development and Drug Interactions: Table of Substrates, Inhibitors and Inducers . Web link Accessed 11 June 2015:  
<http://www.fda.gov/Drugs/DevelopmentApprovalProcess/DevelopmentResources/DrugInteractionsLabeling/ucm093664.htm#inVivo>

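### Section 3.9.2.1 names rifampin as a strong CYP3A inhibitor, although Section 3.10.2 and Appendix 3 class it as a strong inducer; a minor error to correct in the text

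*Combined protocol and SAP*

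**What the plan says.** Section 3.9.2.1 of the combined protocol and SAP gives two examples of strong CYP3A inhibitors: "Avoid coadministration of strong CYP3A inhibitors (such as itraconazole and rifampin) with acalabrutinib on study, if possible". It then sets out what to do if such a drug is needed. The first step is "If moderate or strong CYP3A inhibitors are required on study, monitor subjects for toxicity". A bullet below, for strong or moderate inhibitors, adds consultation and a dose step: "the Medical Monitor should be consulted before use, and a dose reduction of acalabrutinib to 100 mg PO daily or temporarily holding acalabrutinib" (the reduction or hold is something to weigh, not a requirement).

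Section 3.10.2 uses the same two drugs but puts them in opposite classes. For inhibition it reports that "itraconazole increased exposure by approximately 5-fold". For induction it warns that "concomitant administration of acalabrutinib with a strong CYP3A inducer, rifampin decrease acalabrutinib exposure and could reduce efficacy".

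Appendix 3 has one column for strong inhibitors and one for strong inducers. Rifampin stands in the inducer column only, with a footnote that also marks it as an inducer of P-glycoprotein.

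The synopsis covers both classes in one sentence: "The concomitant use of strong inhibitors/inducers of CYP3A4 (see Appendix 3) should be avoided when possible (see Section 3.10.2". Section 3.10.2 has an equivalent sentence, followed by "If a subject requires a strong CYP3A4 while on study, the subject should be monitored closely for any potential toxicities", where the noun after CYP3A4 is missing.

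**The concern.** Inhibitors and inducers of CYP3A call for opposite responses. An inhibitor raises acalabrutinib exposure, so watching for toxicity and lowering or pausing the dose makes sense. An inducer lowers exposure, so the worry is loss of effect. Section 3.9.2.1 is an operative co-medication section. By placing rifampin among the inhibitors, it lets a reader conclude that the inhibitor steps apply to rifampin.

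If a patient needed rifampin during treatment and the site followed that reading, it would look for toxicity and consider a lower dose or none. Either would add to an exposure loss that Section 3.10.2 itself links to reduced efficacy. No other section gives a rule to fall back on: the synopsis and Section 3.10.2 say to avoid strong inducers when possible, and nothing says what to do when one cannot be avoided.

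**Working it through.** This is a comparison of texts; the plan states no figure to reproduce.

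**Class given to rifampin**

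| Place | Class | Stated effect on acalabrutinib |
|---|---|---|
| Section 3.9.2.1 | strong inhibitor, beside itraconazole | none stated |
| Section 3.10.2 | strong inducer | exposure falls; efficacy could fall |
| Appendix 3 | strong inducer only | none specific to acalabrutinib |

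Two places agree, and one of them states the direction of the effect. Section 3.9.2.1 is the outlier. Because Section 3.10.2 pairs the same two drugs as one inhibitor and one inducer, the likely explanation is that the words for inducers dropped out of Section 3.9.2.1.

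**What each instruction in Section 3.9.2.1 would mean for rifampin**

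1. Avoid if possible: correct for an inducer as well.
2. Monitor for toxicity if required: wrong direction, since exposure falls.
3. Consult the Medical Monitor before use: useful, and likely to catch the error.
4. Consider 100 mg daily or a hold: wrong direction.

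Steps 2 to 4 are written for inhibitors and do not name rifampin. They reach it only through the mistaken example in step 1.

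**Size of the dose prompt**

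- Starting dose (Section 3.8, dose reduction schedule): 100 mg twice daily = 200 mg/day.
- Dose to be considered (Section 3.9.2.1): 100 mg/day.
- Ratio: 100 / 200 = 0.50, which is also the lowest dose that Section 3.8 permits. A hold is no dose.

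**Length of the window**

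- Acalabrutinib is planned for days 1 to 21 of 3 cycles (synopsis, Study Design): 3 × 21 = 63 scheduled days.
- Need at baseline without a possible switch is excluded (Section 3.3.2, criterion 27), so only a drug started on study is at issue.

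**The incomplete sentence in Section 3.10.2**

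It follows a sentence about both inhibitors and inducers, so without its noun it could be read as toxicity monitoring for either. The matching sentence in the synopsis says inhibitor, which shows what was meant.

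**The case against.** The strongest reply is that nothing in Section 3.9.2.1 tells a site to reduce acalabrutinib for rifampin. The drug appears only in the sentence on avoidance, which is right for an inducer too, and the dose rule is correct for the inhibitors it addresses. To go wrong, a site must have a patient newly in need of rifampin within the 63 days, find no alternative, overlook Section 3.10.2, Appendix 3 and the drug list linked in the same paragraph, consult a Medical Monitor who also misses the error, and then act on a step that is only to be considered. This stands, and it is why the point is minor. It does not make the example correct.

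Three stronger readings are tempting, and the documents do not support them.

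- A reader might infer a contradiction over true inhibitors, because the synopsis and Section 3.10.2 keep only avoidance and monitoring and leave out consultation and reduce-or-hold. This is an omission. The step is present in Section 3.9.2.1, and Section 1.3.3 sends readers to Section 3.9.2 for interaction guidance. A cross-reference would help but is optional.
- A reader might put a figure on the exposure loss from Appendix 3: "A strong inducer is defined as an inducer that results in" a fall of at least 80% in a substrate's AUC. That defines a class of drugs; it is not a measurement for acalabrutinib. Section 3.10.2 gives the direction for rifampin and no size.
- A reader might conclude that reducing or holding acalabrutinib with an inducer should be forbidden. The documents give no dosing rule for inducers, and a ban would remove an option that the Medical Monitor could weigh.

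Nor does every section say to avoid inducers. Section 3.9.2.1 says it only for inhibitors and the misnamed rifampin; avoidance of inducers as a class is in the synopsis and Section 3.10.2.

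**Conclusion.** The classification of rifampin in Section 3.9.2.1 is wrong as written; this is certain from the protocol's own text. The consequence is narrow and the severity minor. It arises only if rifampin becomes unavoidable during the 63 scheduled days and the reader applies the inhibitor steps to it. The prompt would then be to consider half the starting dose, or none, for a drug that lowers exposure. The protection is avoidance if possible, exclusion criterion 27 for need at baseline, and consultation of the Medical Monitor before use.

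The number of patients who might need rifampin is not given and none is assumed. No size is claimed for the exposure loss. The Simon two-stage rule, its error rates and the analysis of complete response are not affected.

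**What to change.** At the next amendment:

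1. In Section 3.9.2.1, reword the example to: *strong CYP3A inhibitors (such as itraconazole) or strong CYP3A inducers (such as rifampin)*.
2. In the same section, state that toxicity monitoring and the step of considering 100 mg daily or a hold apply to inhibitors only.
3. Add that the Medical Monitor is to be consulted before use if a strong inducer cannot be avoided. Section 3.9.2.2 already does this for drugs that carry a risk of torsades and have no alternative. Do not add an absolute ban on holding acalabrutinib.
4. In Section 3.10.2, restore the word *inhibitor* after CYP3A4 in the sentence on drugs required on study.

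Optionally, add a cross-reference to Section 3.9.2.1 in Section 3.10.2 and the synopsis.

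The cost is a few lines of wording. The one added step is consultation for an unavoidable strong inducer. It is new for carbamazepine, phenytoin and St John's wort; for rifampin the current text, read literally, already asks for it. No visit, test or data item is added.

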### **3.9.2.2 QT Prolonging Agents**

Therapeutic plasma acalabrutinib concentrations after a 100-mg dose or supratherapeutic plasma acalabrutinib concentrations after a 400-mg dose in healthy subjects did not prolong the QTc interval in a thorough QT study.

Medications known to cause Torsades des Pointes should be avoided. Refer to the Arizona CERT website ([http://www.azcert.org/medical-pros/drug-lists/list-01.cfm?sort=Generic\\_name](http://www.azcert.org/medical-pros/drug-lists/list-01.cfm?sort=Generic_name)) or similar websites for a list of these medications. If no alternative treatment is available, the Medical Monitor must be consulted.

Any medications known to cause QT prolongation may be used with caution; periodic monitoring with electrocardiograms (ECGs) and electrolytes should be considered.

### **3.9.2.3 Drugs That May Have Their Plasma Concentration Altered by Acalabrutinib**

Acalabrutinib is a substrate for breast cancer-related protein (BCRP). Acalabrutinib coadministration may increase exposure to BCRP substrates by inhibition of intestinal BCRP. Use caution with coadministered, oral, narrow therapeutic index BCRP substrates.

### **3.9.2.4 Antiplatelet Agents and Anticoagulants**

Patients receiving antiplatelet or anticoagulant therapies in conjunction with acalabrutinib may be at increased risk of hemorrhage and should be monitored for signs of bleeding, as described in section 1.4.2.1.

### **3.9.2.5 Surgery**

Patients who require surgery for any reason while on study are recommended to withhold acalabrutinib for 3-7 days pre- and post-surgery, depending upon the type or surgery and the

risk of bleeding. Patients must have recovered adequately from any toxicity and/or complications from the intervention before the first dose or before restarting acalabrutinib.

### **3.10 PRECAUTIONS**

#### **3.10.1 Dietary Restrictions**

Acalabrutinib can be taken with or without food. There are no dietary restrictions for R-ICE.

#### **3.10.2 Drug-drug Interactions & Infusion Reactions**

Acalabrutinib is metabolized by CYP3A. At the systemic exposure levels expected in this study, acalabrutinib inhibition of CYP metabolism is not anticipated.

Concomitant administration of acalabrutinib with a strong CYP3A and P-glycoprotein (P-gp) inhibitor, itraconazole increased exposure by approximately 5-fold. Conversely, concomitant administration of acalabrutinib with a strong CYP3A inducer, rifampin decrease acalabrutinib exposure and could reduce efficacy. Consequently, the concomitant use of strong inhibitors/inducers of CYP3A (see Appendix 3) should be avoided when possible.

If medically justified, subjects may be enrolled if such inhibitors or inducers can be discontinued or alternative drugs that do not affect these enzymes can be substituted within 7 days before first dose of study drug. If a subject requires a strong CYP3A4 while on study, the subject should be monitored closely for any potential toxicities.

The effect of agents that reduce gastric acidity (eg, proton pump inhibitors or antacids) on acalabrutinib absorption was evaluated in a healthy volunteer study (ACE-HV-004). Results from this study indicate that subjects should avoid the use of calcium carbonate-containing drugs or supplements for a period of at least 2 hours before and at least 2 hours after taking acalabrutinib. Use of omeprazole, esomeprazole, lansoprazole or any other proton pump inhibitors while taking acalabrutinib is not recommended due to a potential decrease in study drug exposure. However, the decision to treat with proton-pump inhibitors during the study is at the investigator's discretion, with an understanding of the potential benefit to the subject's gastrointestinal condition and a potential risk of decreased exposure to acalabrutinib.

Although the effect of H2-receptor antagonists (such as famotidine or ranitidine) on acalabrutinib absorption has not been evaluated, if treatment with an H2-receptor antagonist is required, the H2-receptor antagonist should be taken approximately 2 hours after an acalabrutinib dose.

Infusion reactions related to rituximab, etoposide, ifosfamide, or carboplatin should be managed according to the package insert and/or institutional standard of care.

#### **3.10.3 Contraception Requirements**

##### **Contraception Requirements for Women:**

The following are acceptable measures to avoid becoming pregnant:

- Abstinence (not having sexual relations with a person of the opposite sex)
- Implantable hormone (e.g. Norplant)
- Intrauterine Device (IUD)
- Male partner has had a vasectomy
- Female sterilization
- Hormonal injection
- Oral contraceptives
- GnRH Agonists (zoladex, triptorelin, leuprolide)-these agents are only effective if they have been in continuous use for at least 3 months

Participants must use contraception, at least starting at screening, before starting study treatment unless they abstain from sexual intercourse. Participants must use contraception during study treatment and for at least 90 days after stopping study treatment.

Female participants should not become pregnant, breastfeed, or donate an egg for at least 90 days after the last dose of study medication. If female participants become pregnant while participating in the study or within 1 year of completing study treatment, they should inform their study doctor immediately.

#### **Contraception Requirements for Men:**

One of the following forms of contraception should be used by men or their female partner of childbearing potential:

- Abstinence (not having sexual relations with a person of the opposite sex)
- Implantable hormone (e.g. Norplant)
- Intrauterine Device (IUD)
- Vasectomy
- Female sterilization
- Hormonal injection
- Oral contraceptives

Male participants must use contraception during study treatment and for at least 90 days after stopping study treatment. Participants should also refrain from donating semen during therapy and for at least 1 year after stopping the therapy.

There is theoretical concern that study treatment can result in sperm abnormalities and/or can transmit harmful substances in their semen during sex. Therefore, males must remain abstinent or use a condom, even if they have undergone a vasectomy.

If a female partner becomes pregnant or suspects becoming pregnant during study treatment or within 1 year after completing study treatment, the Study Doctor must be informed immediately. The study Doctor may want to follow the pregnancy and may ask the female partner to sign a consent form so they can collect information about the outcome of the pregnancy.

